10 STATISTICAL METHODS

Statistical considerations are briefly described below.

More details on the analysis and presentation of study results will be provided in the statistical analysis plan (SAP). The SAP will be finalized prior to the unblinding of treatment allocation codes.

Descriptive statistics will be used to summarize all data collected from this study, with inferential statistics provided for the primary and secondary endpoints. Unless stated

This document contains confidential information. It is intended solely for the use of the principal investigator, co-investigators, staff, appropriate institutional review boards or ethical committees, and other required regulatory bodies.

otherwise, the term "descriptive statistics" refers to number of subjects (n), mean, median, standard deviation (SD), standard error of the mean (SEM), minimum, and maximum for continuous data, and frequency tables with counts and percentages for categorical data. The term "treatment group" refers to the randomly assigned IMP, either AG013 or placebo, each topically applied three times daily.

For change from baseline calculations, "baseline" refers to the last measurement obtained prior to the first dose of IMP. Study days will be defined relative to the Baseline Visit (Day 1 of CRT).

All available assessments of oral mucositis (OM) will be used to derive efficacy endpoints (duration, incidence and onset of OM), including WHO severity grades recorded twice per week during the treatment phase (start of CRT until 14 days after the last CRT dose) and weekly during the short term follow-up period (4 weeks after the end of CRT) to capture resolution of OM, as required.

Adjustment for multiple significance testing will be performed using a hierarchical closed testing procedure to control the overall Type 1 error rate at 5%. If the primary efficacy endpoint demonstrates a statistically significant treatment effect (two-sided $p \le 0.05$), secondary efficacy endpoints will be tested sequentially at the same level 0.05 in a prespecified order (as listed below). The process continues until the first time the p-value exceeds 0.05, at which point testing stops and no further significance may be claimed.

Tabulations of summary statistics, graphical presentations, and statistical analyses will be performed using SAS[®] Software (Version 9.3 or higher).

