To ensure that primary efficacy results are robust, sensitivity analyses will be performed using alternative methods for the analysis of duration of severe OM in both the ITT, mITT and PP populations. These methods will include calculations based on the number of days with grade 3 or 4 mucositis throughout the active treatment phase (from start of CRT until 14 days after completing CRT), and the use of various imputation strategies for gap days (i.e., days between twice weekly assessments). In particular, imputation of last observation carried forward and worst-adjacent values will be employed for subjects with missing or incomplete data.

Secondary Efficacy Endpoints:

Statistical methods for the calculation and analysis of secondary efficacy endpoints are provided below. For each endpoint, significance testing will evaluate the superiority of AG013 compared to placebo; two-sided tests will be used to reject the null hypothesis (no difference between groups) in favor of the alternative hypothesis (there is a difference between groups). All efficacy analyses will be performed for the mITT population and stratified by randomization factors (region, cisplatin regimen and HPV status). To control the experiment-wise Type 1 error rate at 5%, significance tests will be performed in the hierarchical order listed here.

Time to onset of severe OM: Time to onset of severe OM (WHO grade 3 or 4) will be calculated as the elapsed time (in days) from the start of CRT until the date of first OM assessment grade 3 or 4. Subjects who do not experience an event by the end of the OM assessment period will be censored on the date of last OM assessment. Subjects with no post-baseline OM assessments will be censored on Day 1. Kaplan-Meier estimation methods and the stratified log-rank test will be used to compare time-to-event distributions and test whether or not AG013 delays the onset of severe OM.

Incidence of severe OM: The incidence of severe OM (WHO grade 3 or 4) will be calculated as the number of subjects with at least one OM WHO grade 3 or 4, divided by the number subjects in the treatment group. Subjects with no OM assessments will be assumed to have severe scores. Subjects who die or withdraw without experiencing OM grade 3 or 4 will also be assumed to have severe scores. A stratified CMH test (general association statistic) will

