Analgesic use: Use of analgesics to control oral pain (parenteral, per oral, or transdermal) will be examined by displaying number and percentages of subjects in each treatment group taking: 1) topicals, 2) OTC analgesics, 3) PO opioids, 4) parenteral opioids. Also, PO and parenteral opioids will be combined to form a category for all opioids. Treatment group differences in proportions will be evaluated using a Chi-square test.

Exploratory Efficacy Endpoints

The effects of AG013 will be explored further on the basis of the following:

This document contains confidential information. It is intended solely for the use of the principal investigator, co-investigators, staff, appropriate institutional review boards or ethical committees, and other required regulatory bodies.
Descriptive statistics will be presented for the incidence of severe mucositis (WHO grades 3 or 4) within subgroups receiving each of the following cumulative radiation doses: 30 Gy, 40 Gy, 50 Gy and 60 Gy.

For each subject, oral mucositis severity scores (WHO grades 0-4) at each time point will be used to calculate area-under-the-curve (AUC) using the trapezoidal rule. Average AUC severity-by-time curves will be generated and plotted for each treatment group, and compared using the Wilcoxon rank-sum test.

Genomic characteristics of responders will be summarized and compared with non-responders.

Frequency and duration of RT interruptions: The number of subjects in each treatment group with an unplanned break in radiotherapy during the 7- to 9-week regimen will be tabulated. Subjects with an interval of 5 days or more without an administration of radiotherapy, or who discontinue radiotherapy prior to completing the planned RT regimen, will be considered to have an unplanned break in RT. The duration of unplanned RT interruptions (in days) will also be summarized by treatment group using descriptive statistics. For subjects who prematurely discontinue radiotherapy, the time from the last dose of RT to the prescribed end date of the regimen will be used in the calculation. The number of unplanned office visits, ER visits, hospitalizations, and non-prophylactic gastrostomy tube placements (US sites only) in each treatment group will be tabulated.

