8. ANALYTICAL PLAN AND STATISTICAL METHODS

8.1 GENERAL CONVENTIONS AND STATISTICAL CONSIDERATIONS

All statistical analyses will be performed and data appendices will be created using the SAS system version 9.4 or higher.

Summary statistics for continuous variables will include number of patients with nonmissing values, number of patients with missing values, mean, standard deviation, median, Q1 (quartile 1), Q3 (quartile 3), minimum and maximum values.

Summary tables for categorical variables will include number and percentage of patients for each category. If not specified additionally, number of patients with non-missing values will be the denominator for percentage calculation. The number of patients with missing values will be presented.

All the analyses will be run displaying by treatment arm and overall.

Unless otherwise stated, all statistical tests will be performed using two-sided tests at the 5% significance level.

If necessary, the statistical analytical plan and statistical methods section may be updated before the database lock. Any changes in statistical methods that may have an impact on the primary conclusions drawn from this clinical trial will be described in an amendment to the protocol. All other changes in the statistical plan will be described in section 9.8 of the clinical study report (CSR). An explanation will be provided for deviations from the planned analysis.

After the last subject completes the end of the short term follow-up phase the database will be locked and the study will be unblinded for the purpose of the statistical analysis. Evaluation of all efficacy and safety endpoints will occur. Evaluation of PK and PD endpoints will occur at a later stage, as well as the genomic analyses. Note: the PD and genomic analyses will only be performed if the study has a positive efficacy outcome. The overall tumor response to chemoradiation therapy will be evaluated following the second database lock after the last subject completes the long term follow-up phase (i.e. 12 months after the last dose of CRT).

A full study report will be written after completion of the statistical analysis including the evaluation of the efficacy and safety endpoints as described in Section 10.1. The PK data and overall tumor response to chemoradiation therapy will be described in an addendum to the study report, as well as PD endpoints and genomic analyses (in case of positive primary endpoint) after (a) later database lock(s).

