8.7.2 ANALYSIS OF KEY SECONDARY EFFICACY ENDPOINTS

Statistical methods for the calculation and analysis of secondary efficacy endpoints are provided below. For each endpoint, significance testing will evaluate the superiority of AG013 compared to placebo; two-sided tests will be used to reject the null hypothesis (no difference between groups) in favor of the alternative hypothesis (there is a difference between groups). The analysis of all key secondary efficacy endpoints will be performed for the ITT, mITT and PP populations.

Note: The OM assessment period includes all OM Assessments performed, including the short-term follow-up period.

To control the experiment-wise Type 1 error rate at 5%, significance tests of the key secondary efficacy endpoints will be performed in the hierarchical order listed below. As specified in the protocol, the mITT population will be the main analysis and guide the hierarchical order of testing. To support these results, the same analyses will be repeated for ITT and PP populations. Each analysis will control for stratifications factors. All the analyses described below will be performed for the purpose of displaying summary statistics, but once the first in the sequence of tests yields a p-value that exceeds 0.05, the nominal p-value for this and subsequent endpoints in the series will be declared non-significant.

Time to onset of severe OM: Time to onset of severe OM (WHO grade 3 or 4) will be calculated as the elapsed time (in days) from the start of CRT until the date of first OM assessment grade 3 or 4. Subjects who do not experience an event by the end of the OM assessment period will be censored on the date of last OM assessment. Subjects with no post-baseline OM assessments will be censored on Day 1. Kaplan-Meier estimation methods and the stratified log-rank test will be used to compare time-to-event distributions and test whether or not AG013 delays the onset of severe OM. The log-rank test will be stratified by cisplatin regimen, HPV status and region. Below is the sample SAS code that performs the intended analysis:

```
proc lifetest
```

```
data=test;
time Time_to_Onset*censor(1);
strata CIS_GRP HPV REGION / group=TRTPN;
run;
```

Incidence of severe OM: The incidence of severe OM (WHO grade 3 or 4) will be calculated as the number of subjects with at least one OM WHO grade 3 or 4, divided by

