8.7.3 ANALYSIS OF OTHER SECONDARY EFFICACY ENDPOINTS

Cumulative radiation dose to development of severe oral mucositis: Total cumulative dose of radiation (in Gy units) until the date of first severe OM (WHO grade 3 or 4) will be calculated for each subject and summarized by treatment group using descriptive statistics in the mITT population. Similarly, the cumulative radiation dose up to the first observed ulcerative oral mucositis (WHO grades 2-4) will be tabulated. If a subject does not experience severe OM during the study, the full cumulative radiation dose will be used. The difference between treatment groups will be evaluated using the stratified CMH test (with modified ridit scores). This test will determine whether the AG013 group achieved a higher cumulative radiation dose before onset of severe OM, compared to the placebo group.

Patient-reported pain: The average of patient-reported MTS scores, graded on a scale from 0 (no soreness) to 4 (extreme soreness), will be summarized by treatment group during each study week as well as for the last 7 days of treatment in the mITT population.

The difference between treatment groups will be evaluated using the stratified CMH test (with modified ridit scores) to determine whether or not AG013 reduces pain.

Other Diary Outcomes: For other diary items: overall health, limited in swallowing, drinking, eating, talking and sleeping, overall soreness and diarrhea descriptive statistics will be produced for each treatment and by study week as well as for the last 7 days of treatment in the mITT population. However, no significance tests will be performed.

Analgesic use: Use of analgesics (parenteral, oral, or transdermal) to control oral pain will be examined by displaying number and percentages of subjects in the mITT population taking:

- Topicals such as viscous lidocaine
- OTC analgesics such as acetaminophen or ibuprofen
- PO opioids such as Vicodin or Percocet
- Parenteral opioids such as morphine or Fentanyl

Also, PO and Parenteral opioids will be combined to form a category for all opioids. Pvalues for all opioids and parenteral opioids will computed using the stratified CMH test (with modified ridit scores).

All the patient-level secondary endpoints will be listed together with the primary endpoint. Listings of radiation therapy data, OMDQ, and analgesics will be created as well.

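### The protocol is inconsistent on how far its testing hierarchy reaches; the SAP takes the narrow scope undeclared and leaves the radiation-dose, pain and opioid tests ungated and not labelled nominal.

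*SAP*

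**What the plan says.** **Protocol, broad scope.** The synopsis (Efficacy) says testing of secondary efficacy endpoints is hierarchical, to protect an overall 5%. Section 10 says that once the primary is significant, "secondary efficacy endpoints will be tested sequentially at the same level 0.05 in a prespecified order (as listed below"), stopping at the first p-value above 0.05. Section 10.5, under its secondary endpoints heading, says "To control the experiment-wise Type 1 error rate at 5%, significance tests will be performed in the hierarchical order listed here". The list that follows runs without a break through the five key secondaries to cumulative radiation dose, patient-reported pain and analgesic use. For analgesics it says "Treatment group differences in proportions will be evaluated using a Chi-square test".

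**Protocol, narrow scope.** The synopsis endpoint list and section 10.1.2 attach the label hierarchical only to the five key secondaries. Section 10.1.4 lists radiation dose, pain and analgesics separately, without that label.

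**SAP.** Section 8.7.2 takes the narrow scope: "significance tests of the key secondary efficacy endpoints will be performed in the hierarchical order listed below". It does not restate that the primary must succeed first. Section 8.7.3 tests radiation dose ("This test will determine whether the AG013 group achieved a higher cumulative radiation dose before onset of severe OM, compared to the placebo group"), tests soreness scores that are summarised by study week and for the last 7 days of treatment, and says p-values for "all opioids and parenteral opioids will computed using the stratified CMH test". Under section 8.1, unless otherwise stated, "all statistical tests will be performed using two-sided tests at the 5% significance level". Section 9 lists three departures from the protocol (baseline summaries, laboratory tables, incidence imputation). The scope of the hierarchy is not among them.

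**The concern.** A reader of protocol 10 and 10.5 expects nothing after a failed step to be called significant, and that includes radiation dose, pain and opioid use. Under the SAP, the primary or a key secondary can fail and a p-value below 0.05 on one of these endpoints can still be reported with nothing marking it as nominal. The experiment-wise 5% would then not cover the statement being made.

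Radiation dose to severe OM is the most sensitive case because it overlaps heavily with time to onset of severe OM, the first key secondary. A delay in onset that the hierarchy has declared non-significant could reappear as a higher dose tolerated before onset.

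**Working it through.** **Inputs.** From the documents: overall level 5%; each step two-sided 5%; SAP default two-sided 5% per test. I count three ungated tests: dose to severe OM, all opioids, parenteral opioids. Dose to ulcerative OM is left out because the plan says it is tabulated and the test sentence names only severe OM. Pain is treated separately because the number of pain tests is not stated. The correlation between tests is not given, so it is assumed and varied from 0 to 0.9. All figures are under the global null.

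**Step 1: the stated 5%.** In a fixed sequence, nothing can be rejected unless the primary is. Familywise error is therefore P(primary p ≤ 0.05) = 0.05, however many steps follow. The protocol's figure reproduces under its broad reading.

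**Step 2: the SAP, independent tests.** The gated chain counts as one 5% test, assuming the protocol's primary gate still applies. Three more are added.

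- Familywise error: 1 − 0.95⁴ = 1 − 0.8145 = 0.1855.
- At least one of the three significant while the primary is not: 0.95 × (1 − 0.95³) = 0.95 × 0.1426 = 0.1355.

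**Step 3: correlated tests.** For k two-sided normal tests with common correlation ρ, the chance that none rejects is

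N_k = ∫ φ(z) [Φ((1.96 − √ρ z)/√(1−ρ)) − Φ((−1.96 − √ρ z)/√(1−ρ))]^k dz.

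Familywise error is 1 − N_4. The chance that one of the three is significant without the primary is 0.95 − N_4.

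| Assumed ρ | Familywise error | One of three significant, primary not |
|---|---|---|
| 0 | 18.5% | 13.5% |
| 0.3 | 17.4% | 12.4% |
| 0.5 | 15.6% | 10.6% |
| 0.7 | 13.0% | 8.0% |
| 0.9 | 9.4% | 4.4% |

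A simulation of 500,000 runs agrees within 0.2 points: 15.7% and 9.3% for familywise error at 0.5 and 0.9; 13.7%, 10.6% and 4.3% for the last column at 0, 0.5 and 0.9.

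**Step 4: unequal correlations.** I assumed 0.5 to 0.8 between duration and dose, 0.2 to 0.4 between opioid and OM tests, and 0.5 to 0.7 between the two opioid tests. Simulated familywise error is 14.7% to 17.0%, and the last column is 9.7% to 12.0%.

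**Step 5: pain.** One pain test added gives 1 − 0.95⁵ = 22.6% if independent. An assumed 7 to 10 weekly tests gives 1 − 0.95¹¹ = 43.1% to 1 − 0.95¹⁴ = 51.2%. These are upper-end values, since weekly scores in the same subjects are correlated.

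**Step 6: overlap with time to onset.** Planned RT is single daily fractions of 2.0 to 2.2 Gy (protocol 4.2), so dose at onset is roughly the number of fractions delivered times that amount. Onset after 15 fractions, for example, means 30 to 33 Gy. Several things loosen the link: plans of 50 to 72 Gy, permitted delays and plan changes, RT interruptions, and event-free subjects, who take their full dose in one analysis and are censored in the other. The overlap is heavy, but its size cannot be derived from the documents.

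**The case against.** The case against is substantial on five points.

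- **Placement.** A reader might infer that the SAP removed these tests from a hierarchy in which the protocol had clearly placed them. The documents do not support that. The hierarchical label sits only on the five key secondaries, and the section 10 reference to a list below can be read as pointing to that labelled list. Pain and analgesic use, as described in protocol 10.5, are also not single tests that would fit a fixed sequence. The SAP's scope is one of two readings, and its silence in section 9 is an undeclared deviation only under the broad one.
- **Wording.** A reader might think the SAP introduced confirmatory language for radiation dose. The same sentence stands in protocol 10.5. For analgesics, the SAP plans two p-values where the protocol applied chi-square tests to the proportions generally.
- **Claims.** SAP 8.7.3 does not say that significance will be declared. The 5% level comes from the general default in 8.1.
- **Test count.** Counting a fourth test, on dose to ulcerative OM, goes beyond what the text settles.
- **Duplication.** Correlations of 0.94 to 0.97 between the dose and time-to-onset statistics can be simulated by setting dose to onset day × 5/7 × 2 Gy with one full dose of 66 Gy. That largely assumes the answer.

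All of this stands. It does not remove the problem, because under the narrow reading the 8.7.3 p-values still carry no nominal label. The omission is visible: the same section says no significance tests will be done for the other diary items, and 8.7.2 says which p-values are to be declared non-significant. The authors wrote such limits where they wanted them.

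**Conclusion.** The point holds as an inconsistency about scope and a missing label. The protocol gives two scopes for the hierarchy; the SAP adopts the narrower without recording it and does not restate the primary gate. It leaves at least three tests, plus an unstated number of pain tests, at the default 5%. If those p-values were read as significant, familywise error would exceed the stated 5% at every correlation examined, from about 9% at 0.9 to 18.5% under independence. The part that arises with a non-significant primary is about 4% to 14%. These figures rest on the global null, the assumed correlations, a count of three tests without pain, and the primary gate being applied. It would go too far to say that type I error control is lost: the primary and key secondaries keep a defined testing order, and no claim on the other endpoints is announced. What is missing is the statement that rules such claims out.

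**What to change.** Before database lock:

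1. In SAP 8.7.2, state that the hierarchy is the primary followed by the five key secondaries, and that the key secondaries are tested only if the primary is significant.
2. In SAP 8.7.3, state that all p-values (radiation dose, soreness scores, all opioids, parenteral opioids) are nominal and support no claim of statistical significance. Reword the radiation-dose sentence so that the analysis *describes whether*, rather than determines whether, the groups differ.
3. In SAP 9, record that the hierarchy is narrower than the protocol 10.5 list.

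The alternative is to keep the protocol 10.5 order and extend the fixed sequence with one named test each for dose to severe OM, pain and opioid use, in that order. Familywise error then returns to 5%.

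Either route costs a few sentences and some table footnotes. Data collection and the primary analysis are unchanged. The small downside is that an isolated low p-value on these endpoints can no longer be called significant.
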